Adverse reactions are rare.¹⁸ Nausea, vomiting and diarrhea may occur.²² If gastric irritation occurs, zinc can be consumed with food, but foods high in calcium, phytates and phosphorus should be avoided. . Other symptoms that have been reported are: Hypotension, jaundice, pulmonary edema, edema of the mucous membranes of the mouth and stomach, unusual tiredness or weakness and gastric ulceration followed by perforation.¹⁸

Drug and other gender interactions

The concomitant use of large amounts of fiber, phosphorus or phytates with zinc supplementation may reduce the absorption thereof by formation of non-absorbable complexes; Foods that contain fiber, phosphorus or phytates should be consumed at least 2 hours after the zinc supplement. Large amounts of iron can inhibit intestinal absorption of zinc, so it should be consumed at least 2 hours after ingesting iron supplements.

Zinc may decrease the absorption of penicillin, tetracycline and quinolone.¹⁸

Allergic reaction

Signs of an allergic reaction may include rash, hives, erythema, edema or peeling; fever, wheezing, dyspnea, dysphagia, stertor, labial, lingual or airway edema.²²

Manifestations and management of accidental overdosing or intake

In general, zinc is well tolerated and acute poisoning is rare. Excess zinc in the body interacts with free thiol groups in macromolecules, thereby blocking the active sites of enzymes, coenzymes and membrane receptors.²³

Acute poisoning of zinc sulfate has only been reported by deliberate ingestion,^{24, 25} while chronic poisoning is the result of the excess oral zinc supplement that causes secondary copper deficiency.²⁶

In case studies, the most common effects associated with prolonged consumption of zinc (ranging from 150 mg to 1-2 g / day) include sideroblastic anemia, hypochromatic microcytic anemia, leukopenia, lymphadenopathy, neutropenia, hypocupraemia and hypoferraemia. Patients often recover to normal blood patterns after zinc suspension with or without copper supplements.

Gastrointestinal toxicity: Gastrointestinal irritation seems to be dose related. Symptoms include nausea (20%), xerostomia (12%), gastrointestinal disorders (10%), abdominal pain, vomiting and diarrhea.²² Zinc sulfate in amounts of 2 g / day or more can cause gastrointestinal irritation and vomiting.²⁷ Acute gastrointestinal bleeding was reported in a patient, who required a blood transfusion of 8 units after taking 440 mg of zinc sulfate daily for a week.²⁸

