Neurotoxicity: Zinc concentrations in the human brain remain in a range of less than 600-800 ng / L. The optimal concentration of free zinc in its ionic form in the cells is around 10 ng / L and when it drops to levels less than 0.06ng / L, apoptosis can be activated; while when levels exceed 60ng / L toxicity can be reached.²⁹The symptom that has been reported most frequently is headache.¹⁸

Hematotoxicity: Excessive ingestion of zinc sulfate chronically can induce anemia and leukopenia.¹⁹

Endocrines: Decreased HDL has been reported in men, while alterations in triglycerides have not been reported.²²

Immune: In a study with 11 volunteers it was observed that excess zinc (300 mg per day for 6 weeks) was associated with immunodeficiency and inflammatory response.²³

Toxicity management

Gastric lavage should be avoided, the administration of chelators such as milk, sodium and calcium at a dose of 50 to 75mg / kg / day is recommended.²²

The researchers' response to adverse reactions, allergic reactions and accidental intake are described in the investigator's manual.

Zinc and oral mucositis

The effectiveness of zinc for the prevention of OM was initially studied in patients with head and neck cancer receiving radiotherapy. Ertekin et al.²⁷ established the dose of 150 mg of zinc sulfate daily in adult patients, finding a reduction in the severity of OM. Lin et al.³⁰ administered zinc chelate at a dose of 75 to 100 mg/day in adults with oral and nasopharyngeal cancer, finding a reduction in the development of OM in patients with oral cancer.

Other studies have used zinc sulfate mouthwashes in adults with head and neck cancer in radiotherapy and in patients with acute myeloid leukemia in the hematopoietic progenitor cell transplant protocol, finding that there were no differences between the zinc group and the control group.^{31, 32} Other studies used L-carnosine zinc mouthwashes in adults with head and neck cancer receiving chemo / radiotherapy and in patients with leukemia in the transplant protocol, obtaining a reduction in the severity of the OM.^{33, 34}

To date, only 3 studies have been conducted in patients receiving chemotherapy, (11) one of them was conducted in patients with head and neck cancer; another in patients with myeloid leukemia and the last in patients with myeloid and lymphoid leukemia; being all in adults, who received 150 mg of zinc sulfate daily, resulting in a reduction in the severity of the OM.^{12, 37, 38} (See Table 3).

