Cancer patients will experience pain, limitation and psychological involvement due to oral OM; this debilitating condition also significantly affects nutritional intake, oral care and quality of life, representing up to 21.9% of the reasons for hospitalization.8 OM, if not properly treated or associated with prolonged neutropenia, may end in septic shock and even the death of the patient.

The use of zinc has been studied as a low-cost alternative for OM, so the realization of this study will determine the effectiveness of the use of zinc for the prevention and reduction of complications due to OM in pediatric patients with ALL of the Institute National Pediatrics.

OBJECTIVE

To assess the impact of the use of zinc in the prevention, incidence and severity of oropharyngeal mucositis in patients with acute lymphoblastic leukemia in chemotherapy (induction and consolidation phase) of the National Institute of Pediatrics and the Children's Hospital of Mexico during the period from 2019 to 2020.

SPECIFIC OBJECTIVES

1. Determine the incidence of OM in patients with ALL assigned control group (Group 1: oral care + placebo) versus the intervention group (Group 2: oral care + zinc).
2. Identify if there are differences in OM severity between Group 1 and Group 2.
3. Identify if there are differences in the recovery time of the OM between Group 1 and Group 2.
4. Identify if there is an association between the severity of OM and severe neutropenia in both groups.

HYPOTHESIS

The use of zinc reduces the incidence and severity of OM in pediatric patients with ALL in chemotherapy compared to the control group.

MATERIAL AND METHODS

Type of study: Randomized, double blind clinical trial.

Duration of the intervention: Induction and consolidation phase of chemotherapy (2 to 2.5 months).

Inclusion Period: from August 2019 to May 2020.

Study population

Target population: patients of both sexes from 3 to 18 years of age with newly diagnosed or relapsed ALL during the period from 2019 to 2020.

Study population: patients of both sexes from 3 to 18 years of age with recently diagnosed or relapsed ALL treated by the Pediatric Oncology service of the National Institute of Pediatrics and the Children's Hospital of Mexico during the period from 2019 to 2020.

Selection criteria

Inclusion criteria: Patients aged 3 to 18 years with a recent diagnosis of ALL or relapse who accept by informed consent to participate in the study.

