AGE	Life time elapsed from birth to the current date.	Life time in years recorded in the clinical record.	Quantitative Discreet	Years 0 a 18
SEX	Physiological and sexual characteristics with which men and women are born.	Biological characteristics recorded in the clinical file as female and male.	Qualitative Nominal Dichotomous	1. Female 2. Male

CONFUSORY VARIABLES				
ACUTE LEUKEMIA LYMPHOBLASTICS (LAL)	Neoplastic disease that results from a clonal proliferation of lymphoid precursors (lymphoblasts), which infiltrates bone marrow, produces a variable degree of pancytopenia and can compromise different organs and / or systems.	Type of leukemia recorded in the clinical file according to the immunophenotype.	Qualitative Nominal	1. Pro B leukemia 2. Common leukemia 3. Pre-B leukemia 4. Mature leukemia B 5. T leukemia (precursors) 6. T leukemia (mature)
NEUTROPENIA	Reduction of peripheral blood neutrophil count .	Absolute neutrophil count obtained by laboratory test (blood count).	Qualitative Ordinal	0. Absence of neutropenia 1. Mild: 1,000-1,500 / ml 2. Moderate: 500-1,000 / ml 3. Severe: <500 / ml
OPPORTUNIST INFECTIONS	Infections in immunosuppressed patients, whether of bacterial, fungal or viral origin.	Record of suggestive lesions by C. albicans and determination by means of KOH, suggestive lesions of herpes and determination by PCR, suggestive bacterial lesions and detection through cultures.	Qualitative Nominal	0. Absent 1. Fungal 2. Bacterial 3. Viral

STUDY DESIGN

Double blind clinical trial

Sampling: Sequential non-probabilistic until the required number of participants is completed.

Randomization: sealed envelopes for group assignment.

Sample size calculation

Formula for the difference of proportions (incidence of OM).

$$\frac{[Z_{\alpha} \sqrt{2\pi_1(1-\pi_1)} - Z_{\beta} \sqrt{2\pi_1(1-\pi_1) + 2\pi_2(1-\pi_2)}]^2}{(\pi_1 - \pi_2)^2}$$

Assumptions:

$$\alpha = 0.05$$

$$\text{Power} = 0.90$$

Rambod study findings: The effect of zinc sulfate on prevention, incidence, and severity of OM in leukemia patients undergoing chemotherapy.

$$Z_{\alpha} = 1.96$$

$$Z_{\beta} = -0.84$$

$$n = 86$$

$$\pi_1 = 75\%$$

$$\pi_2 = 47\%$$

$$\pi_1 - \pi_2 = 28\%$$

$$\frac{[1.96 \sqrt{2(0.75)(0.25)} - (-0.84) \sqrt{(0.75)(0.25) + 2(0.47)(0.53)}]^2}{(0.75 - 0.47)^2} = 46$$

41/5000

15% losses = 53 patients per group

Statistical Analysis Plan

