Six randomized patients with a recent diagnosis of childhood cancer who start chemotherapy will be selected, data from the clinical record will be obtained to determine if it meets the inclusion criteria. The patient identified as eligible will be visited at his place of hospitalization or in the outpatient office of the Oncology Service.

The intervention will be assigned under the balanced block scheme. Children will be randomly assigned to each of the two treatment groups using sealed envelopes.

The sequence of procedures and the complete description of the instruments can be found in the Annex "Pilot test applicator manual".

[figure not shown]
Information collection method

A data record sheet will be filled out that includes the patient's identification form (name, age, sex), type of ALL, chemotherapy phase and blood count; which will be obtained from the clinical file. It will also include the table for the determination of the WHO OM scale, the oral hygiene index and the opportunistic infection registry.

Registration and processing method.

[figure not shown]
The data will be recorded in an Epidata database and analyzed using the STATA 14 statistical program.

FLOWCHART 1

In the previous study by Rambod et al. (12), a difference in the incidence of OM of 28% was obtained and from this, for the present study the estimated sample size was 106 subjects.

Complying with one of the principles that govern clinical trials, which is to reduce the risk of the operated subjects to the minimum possible, in case of observing adverse reactions the suspension of the study will be indicated; while if there are no complications, recruitment will continue until a sample size of 53 subjects is met and at this point the intermediate analysis will be performed as shown in Flowchart 2.

ETHICAL CONSIDERATIONS

In accordance with the principles and guidelines established by good clinical practices (BPC), in accordance with the principles set forth in the Helsinki Declaration of 1964 and with the support provided in the General Health Law, in the Regulations of the General Health Law in the area of provision of Health Care Services, which establishes that the individual welfare of the subjects must sometimes prevail in a study, over the interests of science and the community.

This study will be carried out with the strict observation of the recognized scientific principles and respect, handling the affected data anonymously and confidentially.

Consent

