To parents or to those who exercise parental rights of patients, we provide the information related to the study, both verbally and in writing. The master's student made an initial invitation to the parents or guardians of the minor for their child to participate in the study and read the "Informed Consent Letter" to state the purpose of the investigation and make a description of the same. In the case of patients older than 12 years, also read the "Informed Assent Letter". The signature of the parents and the minor is requested freely and voluntarily with the "Declaration of Consent / Informed Consent" after the purpose of the investigation has been understood and doubts have been clarified.

Confidentiality

To verify the confidentiality and privacy of the participants, the data will be stored in databases to which only the researchers of the study have access.

Risk

The study is classified with greater than minimum risk. The administration of zinc in doses of 50-100 mg / day is considered safe, since no adverse effects have been described at that dose.

Benefits

Patients participating in the study will have greater clinical control for the prevention of oropharyngeal mucositis, since they will be collected before the start of chemotherapy and notifications will be received to receive care from the Stomatology service in the case of treatment.

Although no difference is found in favor of the intervention and the necessary sea, the suspension of the study, measures will be taken to ensure that participants of both groups receive benefits by receiving educational oral care talks, identification of signs of OM, as well as Oral hygiene attachments and medications for the treatment of OM.

BIOSECURITY CONSIDERATIONS

In accordance with current regulations, the following is held:

- NOM-052-SEMARNAT-2005

It establishes the characteristics of hazardous waste, also mentions that expired and leftover drugs are considered hazardous waste and therefore, must finally be disposed of responsibly.⁴¹

- General law for the prevention and integral management of waste.

Article 31. The following hazardous wastes and products used, expired, withdrawn from trade or disposed of and which are classified as such in the corresponding official Mexican standard shall be subject to a management plan:

VIII. In accordance with the above, the remaining or expired doses of the drug (zinc sulfate) should be handled as hazardous waste and its disposal will be as follows:

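### Anaemia is named as an effect of chronic excess zinc and a blood count is recorded, but haemoglobin is not a defined variable and no comparison by arm is planned

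*Combined protocol and SAP*

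**What the plan says.** Under Hematotoxicity the protocol states: "Excessive ingestion of zinc sulfate chronically can induce anemia and leukopenia". The section on overdosing says that the effects seen in case studies of prolonged intake, at 150 mg/day and above, "include sideroblastic anemia, hypochromatic microcytic anemia, leukopenia, lymphadenopathy, neutropenia, hypocupraemia and hypoferraemia".

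Information collection method puts on each child's data sheet "type of ALL, chemotherapy phase and blood count; which will be obtained from the clinical file". It does not list the components of the count or say when counts are taken. The Financing section also lists the blood count among the laboratory tests done at the two hospitals.

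In Definition of the variables, one item is derived from the count: the absolute neutrophil count in four classes, listed as a confounder. Haemoglobin, red-cell indices, transfusion and adverse events do not appear. The four specific objectives cover incidence, severity and recovery time of mucositis, and its association with severe neutropenia. The Statistical Analysis Plan gives descriptive statistics, a t-test, a chi-square test and an ANOVA for mucositis over time.

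The text before Ethical Considerations calls for suspension if adverse reactions are seen. Otherwise recruitment continues to 53 subjects, when an intermediate analysis is done. The Risk section rates the study above minimum risk but calls 50-100 mg/day safe, "since no adverse effects have been described at that dose".

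**The concern.** The protocol identifies a blood effect of the study product and collects the laboratory result that would show it, but plans no use of that result. In this population that matters. The protocol's own definition of ALL includes a variable degree of pancytopenia, so a low haemoglobin in one child will naturally be put down to the leukaemia or its treatment. A rule triggered by observed adverse reactions is therefore unlikely to pick up a zinc contribution. The comparison of randomised arms can separate the two, and the plan does not use it.

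At stake is what the trial can say about safety. It describes itself as the first study of zinc for mucositis prevention in children, with no earlier reference dose. If it ends without looking at haemoglobin by arm, it adds nothing on this effect to the literature-based statement in the Risk section.

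**Working it through.** **1. Following the blood count through the plan**

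| Place | What it does with the count |
|---|---|
| Hematotoxicity; overdosing section | Names anaemia, leukopenia and neutropenia as effects of excess zinc |
| Information collection method | Records the count, components unspecified |
| Definition of the variables | Derives the neutropenia class only, as a confounder |
| Specific objectives | Use severe neutropenia only, in relation to mucositis severity |
| Statistical Analysis Plan | Generic between-group tests; no safety outcome named |
| Intermediate analysis text | Depends on adverse reactions or complications; no laboratory measure named |

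Haemoglobin may well be on the sheet. What is missing is the defined variable and the planned comparison.

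**2. Numbers available**

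The plan has 46 per group before losses, and 46 x 1.15 = 52.9, rounded to 53. With 15% lost, 53 x 0.85 = 45 per arm remain. At the intermediate analysis, 53 / 2 gives about 26 per arm before losses.

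**3. Precision of a haemoglobin comparison**

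The documents give no haemoglobin SD. I assume 1.5 to 2.0 g/dL.

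Half-width of the 95% CI = t x SD x sqrt(2/n).

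- n = 26 per arm (t = 2.009, sqrt(2/26) = 0.277): 0.84 for SD 1.5; 1.11 for SD 2.0.
- n = 45 per arm (t = 1.987, sqrt(2/45) = 0.211): 0.63 for SD 1.5; 0.84 for SD 2.0.

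Adjusting for a baseline count, with an assumed correlation of 0.5, multiplies these by sqrt(1 - 0.25) = 0.866. At 45 per arm that gives 0.54 to 0.73 g/dL.

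Difference detectable with 80% power at 45 per arm = (1.96 + 0.84) x SD x 0.211: 0.89 to 1.18 g/dL.

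**4. Dose context**

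The anaemia reports begin at 150 mg/day; the trial gives 50-100 mg/day. Comparing either with the daily requirements in Table 1, which is headed as elemental zinc, needs the tablet strength on the same basis. The Blinding section describes 50 mg zinc tablets, while the variable table and the Maneuver section give the dose as zinc sulfate. Table 2 equates a 220 mg capsule with 50 mg. If the tablet held 50 mg of the salt on that ratio, its content would be 50 x 50/220 = 11.4 mg.

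| Reading | One tablet, requirement 5-10 mg | Two tablets, requirement 12-15 mg |
|---|---|---|
| 50 mg is zinc | 50/10 to 50/5 = 5 to 10 times | 100/15 to 100/12 = 6.7 to 8.3 times |
| 50 mg is the salt | 11.4/10 to 11.4/5 = 1.1 to 2.3 times | 22.7/15 to 22.7/12 = 1.5 to 1.9 times |

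The two readings differ by a factor of 4.4 (220/50), so multiples of the requirement cannot carry the argument. The passages on tablet strength must be reconciled; Annex VIII, which describes the tablets, was not available.

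**The case against.** The strongest reply is that the documents give little reason to expect the harm. The case reports are at 150 mg/day and above, the Hematotoxicity entry speaks of excess, and the dose section puts the toxic range at 1 to 2 g/day. Table 1 also lists 50 to 75 mg/day in children up to 16 for Wilson's disease, and the dose section cites those figures in support of the trial dose. This stands. A reader might infer that anaemia is likely at the trial dose, or that relative to requirement the children approach the adult amounts linked to anaemia. The documents support neither: scaling toxicity by requirement has no source in them, and the tablet strength is ambiguous.

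A reader might also infer that anaemia would certainly go unreported. That is not shown. The data sheet does not exclude haemoglobin, and the t-test is described generally enough to be applied to it. The investigator's manual and Flowchart 2 were not available. The manual is cited for the response to adverse reactions, however, not for their analysis.

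Two further replies have weight. Transfusion will blunt any difference, and precision is modest, particularly at 53 subjects. Both limit what the comparison can show, but neither is a reason to leave recorded data unused. Lastly, the gap is broader than haemoglobin, since no adverse-event variable of any kind is defined. That is true, and a general safety table could hold this item. Haemoglobin deserves separate mention because the effect is named, the test is already recorded, and the disease masks the effect in individual children.

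**Conclusion.** The concern holds as a gap in the analysis plan. Anaemia is a named effect of chronic excess zinc and the blood count is recorded, yet haemoglobin is neither a defined variable nor compared by arm. A zinc contribution therefore has no planned route into the intermediate or final report. This is worth correcting before analysis, but it is not evidence that the dose is harmful.

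The comparison would be a descriptive screen. Under the assumed SD of 1.5 to 2.0 g/dL, it would locate the mean difference to within about 0.8 to 1.1 g/dL at the intermediate analysis and 0.6 to 0.8 g/dL at the end, before any gain from baseline adjustment. A smaller effect could pass unseen, and transfusion would mask part of a real one. The text findings do not depend on these assumptions; only the precision figures do.

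**What to change.** In the variable table and the Statistical Analysis Plan:

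- Define haemoglobin, from the blood counts already recorded, as a safety variable, and list it as a field on the data sheet.
- Summarise it by coded arm (A and B, so that the code need not be broken) at baseline and at the last available count on tablets.
- Give the between-arm difference with its 95% CI, adjusted for baseline where a count before the first tablet exists. State how many children have one, since the documents do not fix the timing of counts.
- Take transfusions from the clinical file and report the number of children transfused per arm.
- Report this at the intermediate analysis and at the end as description, and limit any safety statement to what the interval excludes.

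Mean cell volume and age- and sex-standardised values are optional; standardisation would need reference norms that the documents do not contain. Separately, reconcile the passages that give the tablet strength as zinc and as zinc sulfate.

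The cost is a few fields copied from existing results, some analysis-plan wording and one extra safety table, with no added blood draw or visit. The drawback is a result partly masked by transfusion, which the table should state.

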Descriptive statistics will be used to characterize the population using measures of central tendency and dispersion for continuous variables and distributions of relative and absolute frequencies for categorical variables. Independent t-test and Chi-square test for the difference between the two study groups. Analysis of variance (ANOVA) to compare the two groups with respect to the OM in the five time periods.

METHODOLOGY

Randomization

The randomization will be taught by [name] [name], assigned to the Oncology service, who is unaware of the objective of the study.

The randomization technique will be carried out through sealed envelopes, which will indicate the bottle that will correspond to the patient, identified as treatment "A" and "B". Likewise, to ensure that the groups are balanced, blocks of 6 sealed envelopes containing 3 patients will be made for each group.

Blinding

The patient and the investigator will be blinded; for this, the 50 mg zinc and placebo tablets will be similar in size, color, shape, weight and taste; the bottles will be classified into codes A and B, which in turn will have the same shape, size and color. All of the above will be done through the Pharmaceuticals GREMAR S.A. de C.V., which is a Mexican company that has a line of food supplements located in Mexico City.

An independent investigator (who will be blinded for the purpose of the study) will be requested to receive the medications (zinc / placebo) prepared by the Pharmaceuticals GREMAR S.A. of C.V., so that it provides to the principal investigator only the bottles coded as "A" and "B". At the end of the intervention, the independent investigator will be asked to reveal the coding of the medications to determine which group (Group 1 placebo or Group 2 zinc) corresponds to treatment A and B respectively.

Instruments

WHO OM scale

The oral mucositis scale proposed by the World Health Organization (WHO) in 1979 will be used. This instrument was designed based on objective signs (erythema or ulcer) and subjective signs (mucosal sensitivity, ability to swallow).

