oropharyngeal mucositis, how it relates to chemotherapy and the preventive measures they can perform. Finally, the complications that may occur during the OM will be explained, such as: difficulty in eating, speaking or swallowing, as well as the measures that must be taken to allow adequate recovery.

Parents will be invited to participate in the protocol explaining the objectives of the study, as well as its risks and benefits. In case of accepting to participate, informed consent and assent (in children over 12 years old) will be presented in accordance with the characteristics that are written in it.

The intervention will be assigned under the balanced block scheme. Children will be randomly assigned to each of the two treatment groups using sealed envelopes.

Oral examination, staining of dentobacterial plaque will be performed (the characteristics of the plaque revealing solution are described in the researcher's manual) for the determination of the oral hygiene index and explanation of brushing technique on day 0 of chemotherapy.

Patients who require dental caries treatment will be rehabilitated by the stomatology service according to their stomatological diagnosis and their general condition. A closed bottle containing 100 tablets (treatment A or B) will be provided according to the random assignment. It will be indicated to administer 1 or 2 tablets daily (according to the age of the patient) from day 1 of chemotherapy.

A written reminder will be provided to parents in which they must check each day if the tablet was taken.

Calls will be made every 3 days to verify that oral hygiene and tablet administration are being carried out; In addition, the reminder will be reviewed twice a week and the remaining tablets will be counted in the bottles.

During the course of chemotherapy (induction and consolidation phase) reviews will be performed on days 1, 4, 7, 14 and 21 of each cycle.

Maneuver

Group 1 (oral care + placebo): gentle tooth brushing with a soft bristle brush 3 times a day and mouthwash with baking soda after each meal (1/4 tablespoon of baking soda dissolved in water to make a mouthwash for 3 minutes) plus the consumption of 1 or 2 oral placebo tablets (mannitol) from day 1 of chemotherapy.

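### Suspension depends on adverse reactions being observed, but no described contact asks about symptoms and no listed item records them, so a clean record would be weak evidence

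*Combined protocol and SAP*

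**What the plan says.** **The rule.** The text after Flowchart 1 states that "in case of observing adverse reactions the suspension of the study will be indicated". If there are no complications, "recruitment will continue until a sample size of 53 subjects is met", and the interim analysis follows.

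**The contacts** (Stages of the study and data collection):
- "Calls will be made every 3 days to verify that oral hygiene and tablet administration are being carried out"
- "the reminder will be reviewed twice a week and the remaining tablets will be counted in the bottles"
- Parents keep a written reminder, ticked daily for tablet intake.
- Reviews take place on days 1, 4, 7, 14 and 21 of each cycle. Their content is not itemised; the summary gives these days as the observation times for oral mucositis (OM).

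**The data sheet** (Information collection method). It holds identification, type of leukaemia, chemotherapy phase and blood count. Then: "It will also include the table for the determination of the WHO OM scale, the oral hygiene index and the opportunistic infection registry".

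**Variables, objectives, analysis.** None of the defined variables, the four specific objectives or the planned tests concerns adverse reactions.

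**What the protocol expects of zinc.** Under gastrointestinal toxicity: "Symptoms include nausea (20%), xerostomia (12%), gastrointestinal disorders (10%), abdominal pain, vomiting and diarrhea". The background also names headache, allergic signs, gastrointestinal bleeding, and anemia and leukopenia on chronic excess. On handling: "The researchers' response to adverse reactions, allergic reactions and accidental intake are described in the investigator's manual". The elimination criteria remove patients hypersensitive to zinc or placebo. The Risk section rates the study above minimal risk, but calls the dose safe on the ground that no adverse effects have been reported at it.

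**The concern.** A rule that acts on observed reactions is only as good as the observation behind it. Here every contact with a stated purpose serves hygiene, adherence or OM, and the places where a safety measure would normally appear are silent on symptoms. Whatever comes to light would then depend on a family volunteering it, and on someone writing it down where no item for it is listed.

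Attribution makes this worse. The protocol itself lists xerostomia among the common oral complications of chemotherapy, and I assume that nausea, vomiting and diarrhea also overlap. A volunteered symptom is then easily put down to chemotherapy. Only the same question, asked in the same way in both arms, can show an excess on zinc.

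At stake is the decision to keep recruiting in what the protocol describes as the first study of zinc for OM prevention in children. That decision would rest on a lightly tested absence of complications, and neither the interim look nor the final report would have reaction rates by arm.

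**Working it through.** The plan states no safety figure, so there is none to reproduce. The check is a reading of the plan followed by an illustration.

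**1. Rule against collection.** The rule needs reactions to be noticed and recorded.
- Calls: stated purpose is hygiene and tablet-taking.
- Twice-weekly check: reminder and tablet count.
- Parent reminder: tablet taken or not.
- Reviews: content not itemised; tied to OM in the summary.
- Data sheet: no symptom item listed. The blood count could show anemia, leukopenia or neutropenia, but neutropenia is defined as a confounder, and chemotherapy produces the same changes (assumed).
- Variables, objectives and analysis: no safety item.

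**2. Zinc children at the look.** Randomization is in "blocks of 6 sealed envelopes containing 3 patients will be made for each group". With a single allocation list (assumed), 53 subjects fill 8 blocks (48 subjects, 24 on zinc) and 5 places of a ninth, which add 2 or 3 on zinc. That gives 26 or 27.

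**3. Chance of recording no reaction.** Let r be the true rate of a given reaction due to the tablet, and q the probability that such a reaction is noticed and recorded. The documents give no q, so it is assumed over a range. With n independent children,

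P(none recorded) = (1 − r × q)^n.

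For n = 26:

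| r | q = 1 | q = 0.5 | q = 0.25 | q = 0.10 |
|---|---|---|---|---|
| 5% | 26% | 52% | 72% | 88% |
| 10% | 6.5% | 26% | 52% | 77% |
| 12% | 3.6% | 20% | 45% | 73% |
| 20% | 0.3% | 6.5% | 26% | 59% |

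For example, with r = 10%, q = 1 gives 0.90^26 = 0.065, and q = 0.25 gives (1 − 0.025)^26 = 0.975^26 = 0.52. With n = 27 the same two entries are 5.8% and 50%. The rates of 10%, 12% and 20% echo the background section but are not tied to 50–100 mg/day, so they are illustrative only.

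**4. What a complete clean record could show.** The one-sided 95% upper limit for 0 of n is 1 − 0.05^(1/n):
- n = 26: 10.9%
- n = 27: 10.5%
- n = 53 (the full planned zinc arm): 5.5%

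These limits require q = 1. With passive noticing, they do not apply to the true rate.

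**The case against.** The strongest defence is that the documents do not show collection to be absent. Several parts of it stand.

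- **The sheet list is not exhaustive.** It omits pain and OM recovery days, both defined as variables, so an item missing from the list may still be on the form. That weakens the list as evidence taken alone. Adverse reactions, unlike pain and recovery days, are also missing from the variables.
- **Some material cannot be seen.** The investigator's manual and the pilot manual are not among the public documents, two figures beside the data-collection text are not shown, and the reviews are not itemised. The protocol says that the investigator's manual covers the response to reactions; whether it also covers asking about them cannot be checked. The finding is therefore limited to what the supplied text describes.
- **The sheet is not wholly blind.** The blood count is on it, so a reader who inferred that it has no place for any zinc toxicity would go too far. The gap concerns symptomatic reactions.
- **Passive detection is possible.** A reader might infer that an absence of reactions is built into the design. The documents do not support that: contact is frequent, families can volunteer symptoms, and the hypersensitivity criterion presupposes that some reactions are noticed. In the formula, a clean record is certain only at q = 0.
- **The quoted rates are not forecasts.** Multiplying them by the 53 zinc children of the full arm gives 10.6, 6.4 and 5.3 cases, which a reader might take as expected counts. The rates stand under overdose and accidental intake, where irritation is said to be dose related; elsewhere the protocol calls adverse reactions rare. The look also has only 26 or 27 zinc children.
- **No safety conclusion is planned.** A reader might fear that the trial will declare zinc safe without measuring it. The Risk section's statement is a prior premise, not a planned result.

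None of this supplies a question about symptoms, an item to record the answer, or a comparison by arm.

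**Conclusion.** The point holds in limited form. As described, the plan ties suspension to adverse reactions without describing how symptomatic reactions are elicited, recorded or compared. Under-ascertainment is likely, and a clean record at the look would say little.

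The size depends on assumptions. At a true rate of 10% with 26 zinc children, moving from full elicitation to noticing one reaction in four raises the chance of an empty record about eightfold (6.5% to 52%). The detection fraction and the rate are both assumed. The conclusion also rests on the visible text alone and would shrink if the manual turned out to contain a reporting step. It does not show that reactions would go wholly unseen, or that zinc is harmful at the trial dose. The sponsor should act on it, because it bears on patient safety and is cheap to correct.

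**What to change.** 1. Add to the data sheet a fixed checklist of the symptoms that the background section names for zinc, each with yes/no, date, severity, assessed relation to the tablet, and whether the tablet was stopped.
2. Ask it in identical words in both arms at the existing 3-day calls or twice-weekly tablet counts, with a baseline before the first tablet. Say in the protocol which contacts do this.
3. Add to the Statistical Analysis Plan a tabulation of reactions by arm, at the look at 53 and at the end.
4. If the investigator's manual already elicits reactions, cite it in the protocol and add the data-sheet field and the table.
5. Reconcile the suspension clause with solicited collection. It gives no type, grade, count or relation to treatment, so once symptoms are asked about, chemotherapy symptoms in either arm would meet it literally. No particular stopping rule is proposed here.

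The cost is a short form and about a minute per contact already scheduled, with no new visits. Many recorded events will be unrelated to zinc, which is why they must be read by arm.
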